2 STUDY OBJECTIVES

[figure not shown]
Primary objectives

- To elucidate the change in physical activity as assessed by the distance walked in meters during the 6-minute walking test between baseline and 12 weeks of study drug treatment in sacubitril/valsartan vs. enalapril patients.
- To assess changes in daily non-sedentary daytime activity between baseline and after 12 weeks of treatment in sacubitril/valsartan vs. enalapril treated patients.

Secondary objectives

- To compare the proportion of patients with improved performance ($\geq 30m$) in the 6-minute walking test at week 12 between sacubitril/valsartan vs. enalapril treated patients.
- To demonstrate that sacubitril/valsartan is superior in improving exercise capacity as assessed by the six-minute walk test (6MWT) at week 12 in a subset of patients with baseline six-minute walk distance equal to or less than 300 meters
- To demonstrate that sacubitril/valsartan is superior in improving exercise capacity as assessed by the six-minute walk test (6MWT) at week 12 in the patients with baseline six-minute walk distance between 100-450 meters.
- To assess changes from baseline (week 0) in exercise capacity assessed by means of the 6-minute walking test at weeks 4, 8 and 12

- To compare the effects of sacubitril/valsartan vs. enalapril on patients' symptom progression by means of the Patient Global Assessment (PGA) questionnaire at week 4, week 8 and week 12.
- To assess dynamics of changes from baseline in daily non-sedentary daytime physical activity in sacubitril/valsartan vs. enalapril treated patients in weekly and two-weekly intervals.
- To assess changes from baseline in mean daily non-sedentary daytime physical activity classified by its intensity for sacubitril/valsartan vs. enalapril treated patients after week 4, week 8 and week12.
- To assess the difference in non-sedentary daytime physical activity between sacubitril/valsartan vs. enalapril treated patients during the treatment period (weeks 0 to 12).
- To assess changes from baseline on M6min (an actigraphy-based measure of the peak six minutes of daytime physical activity) in sacubitril/valsartan vs. enalapril treated patients after week 4; week 8 and week 12.

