To demonstrate that sacubitril/valsartan is superior in improving exercise capacity as assessed by the six-minute walk test (6MWT) at week 12 in the patients with baseline six-minute walk distance between 100-450 meters.	Title: Proportion of patients with improved performance ($\geq 30m$) (Shoemaker et al., 2013 , Tager et al., 2014) in the 6-minute walking test and which walked 100-450 meters at baseline Units of measure: descriptive statistics for quantitative data, absolute and relative frequency distributions including 95% confidence intervals. Time frame: baseline (week 0, at randomization) and week 12	Section 9.5
To assess changes from baseline (week 0) in exercise capacity assessed by means of the 6-minute walking test at weeks 4, 8 and 12	Title: Change from baseline in 6-minute walking test Units of measure: descriptive statistics for quantitative data, absolute and relative frequency distributions including 95% confidence intervals. Time frame: baseline (week 0, at randomization), under treatment (week 4, week 8, week 12)	Section 9.5
To assess changes in daily non-sedentary daytime activity between baseline and after 12 weeks of treatment in sacubitril/valsartan vs. enalapril treated patients.	Title: Proportion of patients who show increased levels ($\geq 10\%$ increase) of non-sedentary daytime physical activity at week 12 compared to baseline Description: non-sedentary physical activity is defined as ≥ 178.50 activity counts per minute; the average number of minutes per day spent in non-sedentary physical activity will be calculated over 14 days before randomization (baseline ¹) and the last 14 days of treatment (i.e. week 10 to week 12). Units of measure: descriptive statistics for quantitative data, absolute and relative frequency distributions including 95% confidence intervals. Time frame: baseline ¹ epoch (i.e. week -2 to week 0), end of study ² epoch (i.e. week 10 to week 12)	Section 9.5

Objective	Endpoint	Analysis

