9.5 Analysis of secondary variables

9.5.1 Efficacy variables

For the secondary variable is the proportion of patients with increased level of non-sedentary daytime physical activity at 'end of study' compared to baseline. It will be analyzed by applying a logistic regression model with factors treatment and baseline NYHA class (NYHA II vs. III/IV) and the baseline value as further covariate. The Odds Ratio for the factor treatment and its 95%-confidence interval will be given. The analysis of this secondary variable will be performed in the FAS (with and without imputation of missing values described in [Section 9.4.3](#).) and additionally in the PP population with and without imputation of missing values.

All other secondary efficacy variables will be analyzed descriptively using the statistics for continuous and categorical data described in [Section 9](#) above. Additionally, two-sided tests of significance (with $\alpha = 0.05$) between the two treatment groups will be performed for all secondary endpoints, using appropriate testing procedures. Details to those statistical testing procedures will be defined in the SAP.

All statistical tests of secondary efficacy variables will be on an exploratory basis. Therefore, no multiple testing strategy will apply for these tests

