6.3.6 Secondary Efficacy Analyses

Proportion of patients with improved performance (≥ 30 m) in 6-minute walking test at week 12 compared to baseline. The comparison of patient groups will be carried out using logistic regression model with factors treatment and baseline NYHA class (NYHA II vs. III/IV) and the baseline value as further covariate. The Odds Ratio for the factor treatment and its 95%-confidence interval will be given.

Proportion of patients with improved performance (≥ 30 m) in 6-minute walking test at week 12 compared to baseline in a subset of patients with baseline 6-minute walk distance equal to or less than 300 meters. The comparison of patient groups will be carried out using logistic regression model with factors treatment and baseline NYHA class (NYHA II vs. III/IV) and the baseline value as further covariate. The Odds Ratio for the factor treatment and its 95%-confidence interval will be given.

Proportion of patients with improved performance (≥ 30 m) in 6-minute walking test at week 12 compared to baseline in a subset of patients with baseline 6-minute walk distance between 100-450 meters. The comparison of patient groups will be carried out using logistic regression model with factors treatment and baseline NYHA class (NYHA II vs. III/IV) and the baseline value as further covariate. The Odds Ratio for the factor treatment and its 95%-confidence interval will be given.

Score of 6-minute walking test will be summarised at baseline, week 4, week 8 and week 12. Change from baseline values will be presented. The comparison of patient groups at week 12 compared to baseline will be analyzed using a two sample (independent group) t-test or a non-parametric Mann–Whitney–Wilcoxon (Wilcoxon rank sum) test, where applicable.

Proportion of patients who show increased levels ($\geq 10\%$ increase) of non-sedentary daytime physical activity at week 12 compared to baseline. The comparison of patient groups will be carried out using logistic regression model with factors treatment and baseline NYHA class (NYHA II vs. III/IV) and the baseline value as further covariate. The Odds Ratio for the factor treatment and its 95%-confidence interval will be given.

PGA scores will be tabulated at week 4, week 8 and week 12. The comparison of patient groups at week 4, week 8 and week 12 will be analyzed using a chi-square test or Fisher's exact test, where applicable.

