6.4 Level of Significance, Multiple Comparisons and Multiplicity

All statistical hypotheses will be two-sided and will be performed using a 5% significance level.

No adjustment for multiple comparisons or corrections for multiplicity are planned.

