For the analyses of further secondary and of the exploratory endpoints referring to data at 'end of study' the same algorithm will be applied to create an extra LOCF visit next to the usual Week 12 visit. This additional 'end of study' measure constitutes a conservative approach in handling of missing data and ensures much as possible unbiased and comparable efficacy results.

In case of qualitative (e.g., increased level of non-sedentary daytime physical activity) or semi-quantitative (e.g., PGA) efficacy variables, missing Week 12 values of patients previously dropped out due to hospitalization or death will be substituted by the worst value possible for the respective variable (e.g., increased level of non-sedentary daytime physical activity="No", PGA="much worse").

In the event that any date for Adverse Events is incomplete after Data Management processing and this date needs to be used for a calculation, the following will be assigned for the missing date:

- if no field is available: no imputation will be performed
- if only the year is available:
 - Onset date: day "01" and month of "January" or first dose administration date, whatever occurs after will be imputed
 - End date: day "31" and month of "December" or EOS date, whatever occurs before will be imputed
- if the month and year are available:
 - Onset date: day "01" will be imputed
 - End date: "last day of the month" will be imputed

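### Two overlapping 6MWT subset objectives promise to demonstrate superiority although the protocol makes every secondary test exploratory, and SAP 6.4's blanket unadjusted 5% rule leaves the conflict unresolved

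*SAP*

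**What the plan says.** Two secondary objectives in SAP section 2 are superiority statements. The first reads "To demonstrate that sacubitril/valsartan is superior in improving exercise capacity as assessed by the six-minute walk test (6MWT) at week 12 in a subset", namely those walking 300 m or less at baseline. The second makes the same claim "at week 12 in the patients with baseline six-minute walk distance between 100-450 meters". Both stand in the protocol summary and in protocol Table 2-1, where the second begins "To demonstrate that sacubitril/valsartan is superior in improving exercise capacity as assessed by the six-minute walk test (6MWT) at week 12 in the patients". No other listed objective claims superiority. The two primary objectives only set out to elucidate or assess.

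SAP 6.3.6 gives each subset its own logistic regression on the responder endpoint (improvement of at least 30 m), adjusted for NYHA class and baseline, with an odds ratio and 95% confidence interval.

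On the status of these tests, protocol 9.5.1 states: "All statistical tests of secondary efficacy variables will be on an exploratory basis". It adds that no multiplicity strategy applies to them. The data analysis entry of the protocol summary gives the same label, and protocol 9.4.2 confines confirmatory testing to the primary analysis in the FAS.

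SAP 6.4 says: "All statistical hypotheses will be two-sided and will be performed using a 5% significance level". It continues: "No adjustment for multiple comparisons or corrections for multiplicity are planned". SAP 4.2, like protocol 9.8, prescribes the Hochberg procedure at a familywise 5% for the two primary hypotheses.

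**The concern.** An exploratory test cannot demonstrate superiority, so the protocol disagrees with itself about what a significant subset result may conclude. The SAP, which the analysts will follow, does not settle the matter. It repeats the superiority wording, does not restate the exploratory status in the text available, and tests everything at 5% without adjustment.

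The two subsets overlap: every patient with a baseline of 100-300 m is in both. Neither is tied to the result of the overall 6MWT primary. If that primary were neutral, the SAP read on its own would leave two further 5% tests, each with a written superiority objective that a report could call met. The same SAP sentence, read literally, also removes the Hochberg adjustment from the primaries.

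**Working it through.** **1. The passages side by side**

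| Question | Protocol | SAP |
|---|---|---|
| Wording of the subset objectives | Superiority (summary, Table 2-1) | Superiority (section 2) |
| Status of secondary tests | Exploratory (summary, 9.5.1) | Not stated in 3.2, 6.3.6 or 6.4 |
| Confirmatory tests | Primary analysis only (9.4.2) | Not stated in 6.4 |
| Multiplicity, primaries | Hochberg, 5% (9.8) | Hochberg, 5% (4.2); none (6.4) |
| Multiplicity, secondaries | None, because exploratory (9.5.1) | None, no reason given (6.4) |

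The first two rows conflict within the protocol. The fourth conflicts within the SAP.

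**2. The plan's own figures**

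The plan states no size, power or error rate for either subset test, so only its primary figures can be reproduced. With n = 2(1.960 + 1.282)² SD²/Δ² per arm:

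- 6MWT (Δ 35 m, SD 114 m): 223; with the exact t distribution 224, as stated.
- Activity (Δ 20 min/day, SD 70 min/day): 258; with the exact t distribution 259, as stated.

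The power tables reproduce under Hochberg. For 300 per arm and correlation 0, simulation gives 93.7%, 96.2%, 99.4% and 90.4%, against 93.6%, 96.2%, 99.4% and 90.4% stated. All other rows agree within 0.3 points. The plan's power therefore assumes Hochberg for the two primaries, and the plan gives no rule that carries alpha on to the subset tests.

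**3. Error rate if either subset result is taken as meeting its objective**

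If the tests were independent:

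- Either direction: 1 − 0.95² = 9.75%.
- In favour of sacubitril/valsartan: 1 − 0.975² = 4.94%.

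Because the subsets share patients, the test statistics are positively correlated and the true figures are lower. With A the share of patients at 300 m or less, B the share at 100-450 m and O the share at 100-300 m, the correlation is approximately O/√(A × B). This treats outcome variance as similar across the subsets.

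The documents give no baseline 6MWT distribution. I assumed a normal distribution truncated at zero, with mean 250-450 m and SD 80 or 114 m. Two correlated null statistics were simulated (2,000,000 draws, cut-off 1.96). Selected rows, including both extremes:

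| Mean, SD (m) | A | B | O | Correlation | Either direction | In favour |
|---|---|---|---|---|---|---|
| 250, 80 | 0.73 | 0.96 | 0.70 | 0.84 | 7.5% | 3.8% |
| 300, 114 | 0.50 | 0.87 | 0.46 | 0.70 | 8.3% | 4.2% |
| 350, 114 | 0.33 | 0.80 | 0.32 | 0.62 | 8.7% | 4.4% |
| 450, 80 | 0.03 | 0.50 | 0.03 | 0.25 | 9.6% | 4.8% |

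For example, 0.32/√(0.33 × 0.80) = 0.62. Correlations were computed from unrounded shares.

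Relative to a single test, the inflation is 7.5/5 = 1.5 to 9.6/5 = 1.9 times. It is the same in one direction: 3.8/2.5 = 1.5 to 4.8/2.5 = 1.9.

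**The case against.** The strongest reply is that the protocol already deals with this. Section 9.5.1 makes the secondary tests exploratory, 9.4.2 limits confirmatory testing to the primary analysis, and SAP section 1 says the SAP is based on protocol version 04 and adds detail to it. The 5% level for secondary tests is the protocol's own, and for those tests SAP 6.4 agrees with 9.5.1 that nothing is adjusted. All of this stands. It shows that no false claim is planned. It does not remove the superiority wording from both documents, and it does not reconcile SAP 6.4 with SAP 4.2.

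A reader might infer that the SAP has withdrawn the exploratory label, because SAP 6.6 writes "For the analyses of further secondary and of the exploratory endpoints" as if these were separate classes and SAP 6.1 declares no change of status. The documents do not support that. The phrase names a tier of endpoints in a rule for missing data and says nothing about how secondary tests are to be interpreted. The silence of 6.1 fits better with no change having been made. Parts of the SAP are also not visible (section numbering runs from 3.2 to 3.4), so the absence of the label can be asserted only for the text available.

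A reader might also infer that a stated 5% error rate is breached. It is not. The familywise 5% is stated for the two primary hypotheses only, and nothing is promised for the secondary tests.

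Finally, the two-sided figures count errors in both directions. For a false claim in favour of sacubitril/valsartan, the relevant figures are about half as large, with 2.5% as the benchmark.

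**Conclusion.** The inconsistency is real and should be corrected. Both documents attach their only superiority wording to two overlapping subset objectives that the protocol's own rules make exploratory, and SAP 6.4 as written neither restates that status nor agrees with SAP 4.2 on the primaries.

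The consequence is a risk in reporting. If either subset p<0.05 were taken as its objective met, the chance of at least one false positive would be about 7.5-9.6% in either direction, or about 3.8-4.8% in favour of sacubitril/valsartan. These ranges depend on the assumed baseline distribution; independence sets the upper bounds of 9.75% and 4.94%. They do not count the repeat of each subset model in the FAS without patients who had test-related adverse events (SAP Tables 14.2-8 and 14.2-10).

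No multiplicity adjustment is needed for the subset tests while they remain exploratory.

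**What to change.** In SAP 6.4, replace the blanket statement with text to this effect: *The two primary hypotheses are tested with the Hochberg procedure at a familywise 5% and are the only confirmatory tests. All secondary and subset tests are exploratory, as in protocol 9.5.1; they are reported with nominal p-values and 95% confidence intervals, and no superiority claim is based on them.*

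In SAP section 2, reword both subset objectives so that they begin *To compare*. Make the same change in the protocol summary and Table 2-1 at any further amendment.

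The SAP edit is a few lines, needs no new data or analysis, and should be made before database lock. It removes the practical risk on its own and resolves the conflict with SAP 4.2. The protocol rewording costs more: under protocol 11.1 it needs a written amendment with the required approvals, and last patient last visit has already passed. The sponsor gives up a subset superiority claim that has no alpha behind it.

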3 EFFICACY AND SAFETY ENDPOINTS

3.1 Primary Efficacy Endpoint

Change in distance walked in meters during the 6-minute walking test between baseline and 'end of study'.

Change in mean daily non-sedentary daytime activity between baseline and 'end of study'.

3.2 Secondary Efficacy Endpoints

The secondary efficacy variables are the following:

- 6-minute walking test, proportion of patients with improved performance (≥ 30 m) from baseline (week 0) at week 12
- 6-minute walking test, proportion of patients with improved performance (≥ 30 m) from baseline (week 0) at week 12 in a subset of patients with baseline six-minute walk distance equal to or less than 300 meters
- 6-minute walking test, proportion of patients with improved performance (≥ 30 m) from baseline (week 0) at week 12 in a subset of patients with baseline six-minute walk distance between 100-450 meters.
- 6-minute walking test, changes from baseline (week 0) at weeks 4, 8 and 12
- Proportion of patients who show increased levels ($\geq 10\%$ increase) of non-sedentary daytime physical activity at week 12 compared to baseline
- PGA score at week 4, week 8 and week 12.
- Proportion of patients with improved symptoms of HF as assessed by PGA
- Change from baseline in mean daily non-sedentary daytime activity in weekly and two-weekly intervals
- Proportion of patients at weekly and two-weekly intervals who show increased levels ($\geq 10\%$ increase) of mean daily non-sedentary daytime physical activity compared to baseline
- Change from baseline in mean daily light and moderate-to-vigorous non-sedentary daytime physical activity between baseline and different time points under treatment.
- Total weekly time spent in non-sedentary daytime physical activity.
- Total weekly time spent in light non-sedentary daytime physical activity.
- Total weekly time spent in moderate-to-vigorous non-sedentary daytime physical activity
- Change from baseline in M6min (actigraphy-based measure of the peak six minutes of daytime physical activity).
- Proportion of patients with increased M6min compared to baseline at week 4, week 8 and week 12.

3.4 Safety Endpoints

The following safety variables will be measured:

[figure not shown]
- All AEs, including treatment-emergent adverse events (TEAEs)
- Laboratory data
- Vital Signs
- Treatment exposure and treatment compliance
- Prior and concomitant drug/non-drug therapies
- Physical examination
- Diagnostic evaluations
- Pregnancy and assessment fertility

4 OVERALL STUDY DESIGN

4.1 Overview of Study Design

This is an international (European), randomized, actively controlled, double-blind, double-dummy, interventional study with prospective data collection. The study comprises 6 visits over 14 weeks. Adult patients with symptomatic HFREF (NYHA classes II or III/IV at a 1:1 ratio) managed in an ambulatory setting (i.e. by primary care physicians, office based cardiologists, HF outpatient clinics) will be randomized in a 1:1 allocation to receive sacubitril/valsartan or enalapril during the double-blind period. Actigraphy will be performed during the entire duration of the study by means of a wrist-worn accelerometry device; the device will be worn continuously for two weeks prior to randomization in order to obtain an individual baseline for each patient, and throughout the treatment period of the study (12 weeks). Figure 4-1 depicts the study design along with the treatment and visit schedule.

Figure 4-1 Study design

¹⁻² sacubitril/valsartan or enalapril (double-blind study drugs) will be given at dose levels (up-titration) depending on pre-study ACEI/ARB doses.

³Pre-study ACEI and/or ARB are replaced by study medication after Visit 2. Therefore washout period (WO) of 36 hours is required; it should start 12 hours before Visit 2 (randomization); the first study treatment intake should be 24 hours after Visit 2. All other HF background and CV medications (e.g. beta blockers, MRAs etc.) and symptomatic treatment (e.g. diuretics) the patient has been taking should remain unchanged throughout the study, if possible and medically justified in the judgement of the investigator.

"Background HF medication per local practice": patients must be on stable HF treatment regimen for at least 4 weeks prior Visit 1. After Visit 1, patients shall retain their pre-study HF treatment for another 2 weeks (week -2 to week 0) for baseline actigraphy recording.

4.2 Determination of Sample Size

There are no published data on a possible effect of a drug intervention on physical activity as measured by accelerometer in HFrEF patients. However, Alosco and colleagues observed patients with HF over a period of 12 weeks and reported activity levels at baseline and after 12 months using a similar accelerometry device ([Alosco, Spitznagel et al. 2015](#)). The mean activity time in light intensity was 188 min/day (SD = 56) at baseline and 183 min/day (SD = 58) after 12 weeks. The corresponding values for activity in moderate to vigorous intensity were 46 min/day (SD = 35) at baseline and 41 min/day (SD = 30) after 12 weeks. From these data an average of 234 min/day at baseline and 224 min/day after 12 weeks can be concluded for the non-sedentary daily activity time. The observed standard deviations for sedentary daily activity time were 76 min/day (baseline) and 63 min/day (month 12), respectively. From these values the standard deviation for non-sedentary activity time (which is approximately the same as for sedentary activity time) is estimated as SD = 70 min/day for both time points.

For the present study we assume a mean baseline value of 200 to 230 min/day for both treatment groups. If treatment with sacubitril/valsartan leads to an improvement which is at least 20 min/day higher than the changes under enalapril, this is considered as clinically relevant.

The standard deviation for the changes from baseline is expected not to be larger than the standard deviations at the two respective visits (corresponding to a correlation coefficient of 0.5 between the values at baseline and at week 12 to 14). Accordingly, the standard deviation for the primary endpoint is estimated as SD = 70 min/day for both treatment groups.

Planning a two-sided test (using the t-test model with $\alpha = 5\%$ and 90% power at $\Delta = 20$ min/day) results in 259 patients per treatment group (nQuery Advisor® 7.0). In order to account for non-eligible patients, it is planned to recruit 300 patients per treatment arm, i.e. 600 patients in total.

With respect to other primary endpoint "change in 6-minute walk test between baseline and weeks 4, 8 and 12/week 12", the following sample size considerations apply: From Täger et al. we deduce a minimal important difference of 35 meters at week 12 and a standard deviation of 114 meters ([Täger, Hanholz et al. 2014](#)). Planning a two-sided test with $\alpha = 0.05$ and 90% power for a group difference of 35 meters leads to a sample size of 224 patients per group, which is covered by the planned patient numbers.

After defining the primary hypotheses H1 and H2, to control the familywise error rate at level 5%, the Hochberg procedure will be used to test the primary hypotheses. It will reject both H1 and H2, if both of them are significant at level 5% simultaneously. Otherwise, it will reject H1 if it is significant at level $\alpha/2$, or reject H2 if it is significant at level $\alpha/2$.

Table 9-1 Power of the study considering both the end-points – Considering 259 subjects in each arm

Correlation between the two end-points	Power to reject H1	Power to reject H2	Power to reject any of H1 and H2	Power to reject both of H1 and H2
0	89.7%	93%	98.5%	84.4%
0.2	89.5%	93%	97.6%	85%
0.4	89.4%	93%	96.5%	85.7%
0.5	89.3%	93%	96%	86%

For power calculations, H1 is based on accelerometry data end-point while H2 is based on the 6 minutes walking test end-point.

Table Error! No text of specified style in document.-2 Power of the study considering both the end-points – Considering 300 subjects in each arm

Correlation between the two end-points	Power to reject H1	Power to reject H2	Power to reject any of H1 and H2	Power to reject both of H1 and H2
0	93.6%	96.2%	99.4%	90.4%
0.2	93.5%	96%	99%	90.6%

